### 6.1.1 Design Rationale

The clinical investigation design ensures that the results obtained have clinical relevance, scientific validity and address the clinical investigation objectives. A repeated measure, within subject research design has been employed to utilize each subject as his or her own control as it accommodates the heterogeneity that characterizes hearing impaired populations. Blinding and masking are not appropriate design considerations due to the design and clinical use of the device.

Pediatric subjects seeking treatment with an Osia 2 bone conduction device may present clinically for study inclusion as being either aided or unaided due to the varying etiologies of hearing loss. Consistent with the current indications for use, subjects will be tested in both the aided and unaided listening condition to capture preoperative performance with and without a non-surgical treatment. Since the Osia 2 Sound Processor cannot be utilized in a non- surgical wearing configuration, each subject will be fit with the Baha 5 Power device on a Baha softband according to the Cochlear Baha Fitting prescription. The Baha 5 Power device is most comparable from a sound processing perspective to the Osia 2 Sound Processor. Preoperative parental inventories, tests for frequency specific audibility, as well as speech perception in quiet and noise will

be compared to performance gathered during the 3 and 6 months post-surgical evaluations to demonstrate the effectiveness of the Osia 2 system. All safety events will be gathered for Surgery plus Visits 1 - 5 and quantified by type, frequency and severity to demonstrate the safety profile for the intended study population.

# 6.2 Subjects

Written, informed consent must be obtained from the subject's parent or legal guardian before any study specific procedures are initiated.

A Sponsor representative (employee of Cochlear) will confirm eligibility criteria in accordance to inclusion and exclusion criteria. The representative may be either the Clinical Project Manager, a qualified ENT surgeon, audiologist or qualified subject matter expert. Following consent of a subject, the site must provide a deidentified audiogram to be reviewed by the representative.

Prior to implantation of a subject, the representative must have confirmed eligibility, and all screening and baseline assessments must be completed and entered into the EDC in accordance with the Schedule of Events.

Throughout the duration of the clinical investigation, source document records must be maintained to validate subject data.

### 6.2.1 Inclusion Criteria

Subjects must meet all of the inclusion criteria described below to be eligible for this clinical investigation.

1. Subjects aged 5 to 11 years of age with the following audiometric criterion:

A conductive or mixed hearing loss and still can benefit from sound amplification. The pure tone average (PTA) bone conduction (BC) threshold (measured at 0.5, 1, 2, and 3 kHz) should be better than or equal to 55 dB HL.

#### OR

A profound sensorineural hearing loss in one ear and normal hearing in the opposite ear (i.e., singlesided deafness or "SSD"). The pure tone average air conduction (AC) hearing thresholds of the hearing ear should be better than or equal to 20 dB HL (measured at 0.5, 1, 2, and 3 kHz).

- 2. Prior experience with amplified sound through properly fitted amplification device such as a hearing aid, a CROS device, or a bone conduction device on a softband or sound arc.
- 3. Parent or legal guardian who is willing and able to provide written informed consent for the study participant.

Note: Subjects may include individuals seeking new implantation unilaterally (in one ear) or individuals already implanted with a bone-anchored device seeking a second-side implant (sequential bilateral).

### 6.2.2 Exclusion Criteria

Subjects who meet any of the exclusion criteria described below will not be eligible for this clinical investigation.

- 1. Insufficient bone quality or quantity to support implantation of both the BI300 Implant and the OSI200 Implant.
- 2. Chronic or non-revisable vestibular or balance disorders that could prevent benefit from the device, as determined by the investigator.
- 3. Abnormally progressive hearing loss.
- 4. Evidence that hearing loss is bilateral retro cochlear or bilateral central origin.
- 5. Evidence of conditions that would prevent speech recognition improvement as determined by the investigator.
- 6. Skin or scalp conditions that may preclude attachment of the Sound Processor or that may interfere with the use of the Sound Processor.
- 7. Unable or unwilling to comply with the requirements of the clinical investigation as determined by the Investigator.
- 8. Investigator site personnel directly affiliated with this study and/or their immediate families; immediate family is defined as a spouse, parent, child, or sibling.
- 9. Cochlear employees or employees of Contract Research Organizations or contractors engaged by Cochlear for the purposes of this investigation.
- 10. Currently participating, or participated within the last 30 days, in another clinical investigation involving an investigational drug or device that could impact the safety or effectiveness of the Osia 2 system as determined by the investigator.
- 11. Individuals undergoing simultaneous single-stage aural atresia or microtia repair due to the increased risk of skin complications associated with ear reconstruction.

### 6.2.3 Number of Subjects Required

Sample size for the study is not driven by power requirements for a formal statistical hypothesis test. The planned sample size of 50 subjects will provide data to characterize safety and effectiveness with a reasonable degree of statistical precision. Additionally, the planned sample size will allow for a high probability of observing events of interest. For example, with 50 subjects, the half-width of a two-sided 95% confidence interval for a continuous endpoint based on a t-distribution would be 0.284 units on the effect size scale. Similarly, with 50 subjects, there is a greater than 95% probability of observing one or more events that occur at a population rate of 5.9%.

Stratification of the 50 subjects will include a minimum of 10 subjects with single-sided-deafness. In addition, at least one-third (15) of the subjects represented at the youngest ages (5-6 years) will be implanted with the remaining 35 subjects represented by the other age groups as evenly as possible.

### 6.2.4 Vulnerable Populations

Children aged 5 to 11 years of age who present with conductive or mixed hearing loss (up to 55 dB HL) or single-sided-deafness (SSD) will be recruited for participation in this investigation. Subjects will be recruited from both private practice and university-based hospital locations, geographically distributed across the United States who currently treat patients clinically with the Osia 2 system. The clinical investigation sites will

initiate treatment as part of the study and continue care following study completion as part of standard medical and/or clinical care. Information pertaining to the study objective, visit schedule, and associated procedures will be reviewed in an age appropriate manner with both the potential subject and their parent or legal guardianprior to study participation. Verbal assent will be required for subjects aged 7 – 11 years of age and is documented according to each Institutional Review Board (IRB) requirements. Recruitment must include processes to ensure the investigator discusses the informed consent with all subjects, parent(s)or legal guardian(s) as well as addresses all questions to the individual's satisfaction. Additional measures taken to review the study with potential subjects must be documented in the informed consent process. The IRBs may have additional requirements which must be followed.

The subject's parent or legal guardian will be compensated on behalf of the subject for their time participating in the clinical investigation in alignment with fair market value, and the payment rate and process is detailed within the informed consent.

### 6.2.5 Recruitment and Study Duration

The following subject status definitions apply:

- Enrolled: A subject who has a signed Informed Consent form for the study.
- Screened: A subject who has a signed Informed Consent form and has met the eligibility criteria.
- Screen Fail: An enrolled subject who has been determined to not meet one or more eligibility criteria.
- Participated: An enrolled subject who has met eligibility criteria and has been treated with the Osia 2 System.
- Discontinued: An Enrolled subject who withdrew consent, was discontinued by the Investigator or Sponsor before the expected End of Study visit or was lost to follow-up. Discontinued subjects may still have safety follow-up data collection until their scheduled End of Study visit, for reasons described in section 6.2.6.
- Completed: Enrolled subjects who complete the required treatment and visit schedule.

The recruitment period for the clinical investigation is estimated to be 12 months from the time of first subject consent to recruitment of the last subject.

The expected duration of each subject's participation in the clinical investigation, is anticipated to be 14 to 18 months from the time of informed consent to End of Study Visit 5.

Clinical Investigation completion is last subject last visit. AE recording will continue for each subject until completion of their End of Study visit. Ongoing SAEs and SADEs will be followed for an additional 30 days, or until resolution or stabilization within the 30-day period following End of Study. Management of the SAE/SADE beyond clinical investigation completion will be absorbed into standard clinical and medical care by the participating clinical investigational site.

### 6.2.6 Criteria and Procedures for Subject Withdrawal

Subjects can decide to withdraw from the investigation at any time. The Investigator shall ask the reason(s); however, subjects have the right to withhold their reason if preferred. The reason for withdrawal should be documented in the subject's source files and the case report form (CRF), if provided.

The Investigator or Sponsor may also decide to withdraw a subject from the clinical investigation or stop the use of the investigational device if it is considered to be in the subject's best interests.

Subject withdrawal may be for any of the following reasons:

- Adverse Event (AE)
- Device Deficiency (DD)
- CIP or GCP deviation
- Subject withdrew consent
- Subject lost to follow-up
- Subject death
- Sponsor decision
- Investigator decision
- Other (specify)

If subject withdrawal is due to problems related to the safety or performance of the Osia 2 system, the Investigator may ask for the subject's permission to continue in safety follow up (for example, adverse events and device deficiencies) until their scheduled End-of-Study visit at Visit 5.

If a subject is lost to follow-up, every possible effort must be made by the study site personnel to contact the subject and determine the reason for discontinuation. At least 3 separate attempts taken to contact the subject must be documented.

Participating subjects who are withdrawn/discontinued will not be replaced.

#### 6.2.7 Randomisation Procedures

Not applicable.

#### 6.2.7.1 Blinding Procedures

Blinding is not an appropriate study design consideration based on the design and use of the Osia 2 System.

#### 6.2.8 Post-investigation Medical Care

Following the investigation, subjects will continue with standard of care treatment.

### 6.3 Evaluations and Procedures

For each enrolled subject, the clinical investigation will include Screening and preoperative Baseline procedures, Surgery to implant the Osia 2 device, and 5 post-surgery visits.

### 6.3.1 Screening/eligibility

### 6.3.1.1 Informed Consent

Informed consent and assent, as applicable, will be obtained as outlined in section 9 of this CIP prior to any study procedures taking place.

### 6.3.1.2 Unaided Audiometric Testing

Unaided audiometric thresholds will be obtained for each ear independently, using the standard audiometric technique for pure-tone air and bone conduction testing preoperatively to establish candidacy for participation in the clinical investigation.

• Air Conduction: 500, 1000, 2000, 3000 & 4000Hz

Hearing thresholds that exceed the air conduction limits of the audiometer, where the participant reports feeling the acoustic stimuli, shall be recorded as vibrotactile (VT). Appropriate masking will be employed where required.

• Bone conduction: 500, 1000, 2000, 3000 & 4000Hz

Where the participant reports feeling rather than hearing the acoustic stimuli, the response shall be recorded as vibrotactile (VT). Appropriate masking will be employed where required.

For participants with conductive or mixed hearing loss, the bone conduction PTA will be captured and rounded to the nearest whole number to document audiometric eligibility. For participants with single-sided deafness (SSD), the air conduction PTA will be captured and rounded to the nearest whole number to document audiometric eligibility.

### 6.3.1.3 Medical, Hearing & Device History

• Hearing History will document the subject's history of hearing loss (may be subject reported) and hearing loss etiology.

• Device history will document the subject's history with hearing aids and/or surgical or non-surgical bone conduction technology (may be subject reported).

• Medical History will document the subject's medical history relevant to the conduct of the study.

### 6.3.2 Performance/Effectiveness

### 6.3.2.1 Description of Audiometric Testing

Preoperatively, unaided audiometric thresholds will also be obtained in sound field using narrowband noise. Postoperatively at Device Fitting Visit 2, unaided bone conduction thresholds will be obtained as described in section 6.3.1.2 in the implanted ear to assess the impact of implantation and aid in the fitting of the sound processor. The contralateral ear will be masked accordingly.

• Unaided Sound Field Thresholds: 500, 1000, 2000 & 4000Hz

Aided audiometric thresholds will be obtained preoperatively and in the postoperative aided condition using narrowband noise in sound field. The contralateral ear will be plugged for all tests.

Aided Sound Field Thresholds: 500, 1000, 2000 & 4000Hz

### 6.3.2.2 Description of Speech Perception Testing

### 6.3.2.2.1 Consonant Nucleus Consonant (CNC) Monosyllabic Words

The CNC Word Test (Peterson & Lehiste, 1962) consists of 10 recorded lists of 50 monosyllabic words. For this study, one list will be administered per test condition at 60 dBA at 0° azimuth (S0) in sound field and scored as the number of phonemes and words correct, which will be expressed as a percentage correct when analyzed. Preoperatively, CNC Words will be assessed in the unaided condition as well as the aided condition using the Baha 5 Power on a softband. Postoperatively, CNC Words will be assessed only in the aided condition using the Osia 2 sound processor. Pre and postoperative testing will be completed with the contralateral ear plugged or muffed in an effort to isolate the treated ear.

### 6.3.2.2.2 Bramford-Kowal-Bench Speech-In-Noise (BKB-SIN)

BKB-SIN (Etymotic Research, 2005) is composed of 36 lists of BKB sentences (Bench, Kowal, & Bamford, 1979), spoken by a male target talker amidst four-talker babble. The 36 lists are divided into 18 equally difficult pairs of sentence lists. The list-pairs are composed of 16 to 20 sentences that each have 3 or 4 key words. Target speech is presented at 65 dBA and the level of the noise is varied in 3 dB steps at fixed SNRs, beginning at +21 dB SNR (very easy), and descending to 0 or –6 dB SNR (very difficult), depending on the list. Speech reception threshold (SRT) is calculated in dB, which is referred to as the SNR-50, is defined as the signal-to-noise ratio (SNR) required for the subject to repeat 50% of the key words correctly. One list pair of sentences will be presented at 0° azimuth in the sound field, with babble presented at 0° azimuth (SON0). Preoperatively, BKB-SIN will be assessed in the unaided condition as well as the aided condition using the Baha 5 Power on a softband. Postoperatively, BKB-SIN will be assessed only in the aided condition using the Osia 2 sound processor. Pre and postoperative testing will be completed with the contralateral ear plugged or muffed in an effort to isolate the treated ear.

#### 6.3.2.3 Description of Questionnaires

### 6.3.2.3.1 Speech, Spatial, and Qualities of Hearing Questionnaire (SSQ) for Parents

The Speech, Spatial, and Qualities of Hearing questionnaire (SSQ) from MRC Institute of Hearing Research, UK modified for parental response will be used as a subject self-assessment in three categories:

- 1. Speech hearing rating scale
- 2. Spatial rating scale
- 3. Sound qualities rating scale

#### 6.3.2.3.2 Device Use Questionnaire (DUQ)

A Sponsor-designed Device Use Questionnaire or DUQ will be administered to the subject's parent or legal guardian to determine subjective preferences with regards to device use and satisfaction in a variety of listening environments.

### 6.3.3 Safety Evaluations and Procedures

Safety data will be reviewed in accordance with the Sponsor's standard operating procedures regarding safety events. The risks and anticipated ADEs for the Osia 2 system, as identified in Sections 7.2 and 7.3 below, will be assessed in the clinical investigation via reporting of all AEs/ADEs from the time of subject implantation until subject last visit. Ongoing SAEs and SADEs will be followed for an additional 30 days, or until resolution or stabilization within the 30-day period following End of Study. Management of the SAE/SADE beyond clinical investigation completion will be absorbed into standard clinical and medical care by the participating clinical investigational site.

### 6.3.3.1 Concomitant Medication and Therapies

Concomitant Medications recorded in the CRF includes all prescription medications, routine over-the counter medications, and any use of steroids. Medications used during surgery, vitamins, herbal and natural remedies are not included. There are no further prohibited medications under this clinical investigation. Medications taken for anesthesia purposes during surgery will not be recorded unless their use deviates from normal clinical practice.

### 6.3.4 Detailed Visit Schedule

### 6.3.4.1 Screening

- Written informed consent
- Demographics: Document date of birth and sex
- Eligibility: Confirm subject meets all inclusion criteria and no exclusion criteria. Source documentation must be available before confirming eligibility
- Hearing History: Document history of hearing loss (may be subject reported)
- Device history: Document history with hearing aids and/or surgical or non-surgical bone conduction technology (may be subject reported)
- Medical History: Document medical history
- Audiometric testing: Includes unaided air and bone conduction testing. Must be completed less than 60 days prior to implantation and document single sided deafness or mixed or conductive hearing losses.

#### 6.3.4.2 Baseline

- Audiometric testing: Includes both unaided and aided threshold testing. Must be completed less than 60 days prior to implantation in the aided and unaided condition. The aided condition includes testing with the Baha 5 Power on a softband.
- Speech Perception testing: Includes both unaided and aided testing using CNC words and BKB-SIN sentences. Must be completed less than 60 days prior to implantation in the aided and unaided condition. The aided condition includes testing with the Baha 5 Power on a softband.

• SSQ Parent: Completed interview-style based on everyday listening condition - not aided condition with Baha 5 Power on the day of testing. Must be completed within 60 days prior to implantation.

#### 6.3.4.3 Surgery (day 0)

• Surgical Questionnaire: documentation of surgical procedure completed day of surgery.

#### 6.3.4.4 Visit 1: 2 Week Follow Up

• Surgical follow up: wound and incision check

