#### 6.3.4.5 Visit 2: 4 Week Device Fitting

- Bone Conduction testing: Includes unaided bone conduction threshold testing.
- Device programming: Fitting and programming of the Osia 2 sound processor.
- Sound field thresholds: Includes aided thresholds using the Osia 2 sound processor.

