### 7.2.2 Risks Associated with Implantation of the Study Device

- Pain or discomfort
- Skin irritation near the implant, swelling or redness near the magnet site, skin breakdown
- Sense of numbness or stiffness in the area of the surgery
- Failure of the implant to properly anchor to the skull-bone due to a lack of adequate bone quantity/quality, trauma, infection, generalized diseases and surgical complications
- Other medical complications that may require additional medical treatment, such as:
  - Concurrent CSF leakage: a leak of CSF (cerebrospinal fluid) through the hole in the skull

- Subdural injury: blood vessels near the brain may burst
- Subcutaneous hematoma: bruises and contusions on the skin
- Skin-flap infection, irritation or inflammation
- Extrusion of the device caused by a foreign body under the skin
- Revision surgery to remove the study implant in the event of device failure
- Failure of the implant or sound processor could result in the perception of an uncomfortably loud sound sensation, intermittent sound, or no sound.
- The implanted magnet may affect MRI (Magnetic Resonance Imaging) procedures. The magnet may influence the MRI scanner or the ability of the scanner to detect certain changes. Under certain circumstances removal of the magnet may be necessary prior to MRI scanning.

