### 8.2 Endpoints

### 8.2.1 Primary Endpoint

The primary endpoint is adverse events and serious adverse events Surgery through Visit 4 (6 Months). Events will be summarized by type, frequency, and severity.

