## 10.2 Recording and Handling of Adverse Events

Subjects shall be carefully monitored during the clinical investigation and the investigator should enquire about AEs at investigation visits.

All AEs will be recorded from the time of implantation. AE recording will continue for each subject until completion of their End of Study visit. Ongoing SAEs and SADEs will be followed for an additional 30 days, or until resolution or stabilization of the event, whichever comes first. Management of the SAE/SADE beyond clinical investigation completion will be absorbed into standard clinical and medical care by the participating clinical investigational site.

Source notes should indicate the evaluation for AEs, even if there was none to report. All required AEs will be reported if observed, even if anticipated and/or acknowledged as a risk factor in the consent.

All AEs will have the following information documented: start and stop dates, action taken, outcome, severity and investigators opinion on the potential relationship to the Osia 2 system and study procedures. If an AE changes in severity, the most severe (highest) grade will be captured for that event on the Adverse Events CRF.

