#### 5.1.2 Visit Windows

Unless otherwise specified, visit based assessments will be analyzed for each analysis time point according to the nominal visit entered in the Case Report Form (CRF) regardless of if it is out of window. Windows are defined in the CIP as follows: Visit 1 2 week follow up = +/- 7 days, Visit 2 Device Fitting = +/- 7 days; Visit 3 3 Months +/- 14 days, Visit 4 6 months +/- 14 days, and Visit 5 12 Months +/- 14 days.

St	atistical Analysis Plan	Pa	ge 7 of 13
Sponsor	Study		Version
Cochlear Americas	A pivotal, prospective, multi-center, open- label study evaluating the safety and effectiveness of the Cochlear ™ Osia ® 2 System in a pediatric population		1.0

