#### 5.6.1 Primary Endpoint

The primary endpoint is device and procedure related adverse events Surgery through Visit 4 (6 Months). Events will be summarized by type, frequency, and severity.

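### No standardised implant-site inspection is scheduled once the processor is fitted, so magnet-site skin events in the primary safety endpoint depend on general adverse-event enquiry and incidental observation

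*Protocol*

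**What the plan says.** **Examination of the site.** Protocol Section 6.3.4.4 (Visit 1, week 2) has one entry: "Surgical follow up: wound and incision check". No later visit list names a look at the skin, implant or magnet site. Visit 2 (Section 6.3.4.5, week 4) is the first fitting: "Device programming: Fitting and programming of the Osia 2 sound processor", with bone conduction and aided sound-field testing. Visits 3 and 4 list optional programming, sound-field and speech tests, and questionnaires. Visit 5, at 12 months, is a review of records. The Schedule of Events has no skin or implant-site row; the nearest entry is skin thickness, recorded on the surgical questionnaire on the day of surgery.

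**The risk.** Section 7.2.2 anticipates "Skin irritation near the implant, swelling or redness near the magnet site, skin breakdown". Section 10.1.6 defines no adverse events of special interest.

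**How events are found.** Section 10.2 says that "the investigator should enquire about AEs at investigation visits". It also asks for careful monitoring, and for source notes to show that AEs were evaluated even when there was nothing to report. Section 6.3.4.10 requires AE review at every visit. Section 10.1.1 counts untoward clinical signs as AEs, not only complaints. Section 7.2.3 says parents should be advised to check routinely for skin irritation at the implant site.

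**The endpoint.** Protocol Section 8.2.1 takes all AEs and SAEs from surgery to 6 months; SAP Section 5.6.1 takes those related to device or procedure. A skin reaction to the magnet falls under both. Both documents report what was observed and impute nothing (protocol 8.6.1, SAP 5.6.1.1).

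**Precision.** Protocol Section 6.2.3 states that with 50 subjects "there is a greater than 95% probability of observing one or more events that occur at a population rate of 5.9" per cent.

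**The concern.** The one scheduled look at the site comes before the external magnet is worn. The protocol shows elsewhere that skin matters for this device. It excludes skin conditions that would interfere with the processor and excludes simultaneous ear reconstruction because of skin complications (Section 6.2.2, items 6 and 11). The single SAE in the sponsor's earlier paediatric study concerned a thick skin flap (Section 3.2.2.2). Flap thickness is also a site-initiation topic (Section 7.4). Yet for effects of wearing the processor, no uniform way of looking is laid down.

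Two consequences follow for the primary endpoint. First, a mild or painless change that nobody reports or notices is not counted. There is no control group to share the shortfall, so any under-detection lowers the rate in the device's favour. Second, some sites may look routinely while others only ask. That difference would appear as a site difference in AE rate and would enter the poolability analysis in SAP Section 5.7, which models the proportion of subjects with a procedure- or device-related AE by site.

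**Working it through.** **Step 1: timing.** SAP Section 5.1.2 gives "Visit 1 2 week follow up = +/- 7 days, Visit 2 Device Fitting = +/- 7 days". Taking week 2 as day 14 and week 4 as day 28:

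- Visit 1: days 14 − 7 to 14 + 7, that is 7 to 21.
- Visit 2: days 28 − 7 to 28 + 7, that is 21 to 35.

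An in-window Visit 1 therefore never falls after an in-window fitting; at the extreme they share day 21. The SAP analyses by nominal visit even when a visit is out of window, so the order is guaranteed only for in-window visits.

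**Step 2: what is named after fitting.** Setting the lists side by side:

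| Visit | Named content bearing on the site |
|---|---|
| 1 (week 2) | Wound and incision check |
| 2 (week 4) | None; processor fitted |
| 3 (month 3) | None |
| 4 (month 6) | None |
| 5 (month 12) | None; record review, after the primary window |

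AE review applies at all five visits, but the specific act named for finding AEs is to enquire.

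**Step 3: the plan's own figure.** Inputs: n = 50 and rate p = 0.059 (protocol Sections 6.2.3 and 8.4, SAP Section 4).

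P(at least one) = 1 − (1 − 0.059)^50 = 0.952.

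The stated figure of more than 95% is correct. The rate giving exactly 95% is 1 − 0.05^(1/50) = 0.0582. Both calculations take every event as detected.

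**Step 4: illustration with incomplete detection.** Let s be the probability that a subject with the event is recorded, independently across subjects. The documents give no value for s, so the values below are assumptions.

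P(at least one recorded) = 1 − (1 − 0.059 s)^50; true rate needed for 95% = 0.0582 / s; expected subjects recorded = 50 × 0.059 × s.

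| Assumed s | P(at least one recorded) | True rate needed for 95% | Expected subjects recorded of 50 |
|---|---|---|---|
| 1.0 | 95.2% | 5.8% | 2.95 |
| 0.8 | 91.1% | 7.3% | 2.36 |
| 0.6 | 83.5% | 9.7% | 1.77 |
| 0.5 | 77.6% | 11.6% | 1.48 |

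The 5.9% is the plan's general example for events of interest. It is not an estimate of the skin-event rate, and the table does not make it one.

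**The case against.** A reader might infer that magnet-site events will be found only if a family mentions them. The documents do not support that. Enquiry by the investigator is active, AE review is required at each visit, a negative evaluation must be documented, and a sign seen by staff is an AE without any complaint. Aided testing at Visits 2 to 4 gives staff an opportunity to notice the skin, and parents are to be advised to check it.

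A reader might also infer that these skin events cannot occur before the processor is worn. That is not supported either. Section 7.2.2 lists them among risks of implantation, alongside skin-flap infection, and refers to an implanted magnet, which is present from surgery. The timing argument concerns only the effects of wearing the external part.

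The absence of a schedule row is weak evidence taken alone. The Visit 1 wound check has no row of its own, and the lists for Visits 1 to 4 omit AE review although it is required. The CRFs and the instructions for use are not available here and may prompt a look. The primary endpoint has no hypothesis test (Section 8.3.1), so no formal decision turns on the result, and the sensitivities in the working have no source.

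All of this stands and limits the point. It does not remove it. None of these provisions in the available documents specifies an inspection after fitting. A clinical sign must be seen before it can be recorded, programming at Visits 3 and 4 is optional, and advice to parents is not a study assessment.

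**Conclusion.** The point holds as a cheap improvement, not as an error or a demonstrated bias. After week 2 the plan names no standardised inspection of the implant site. Detection of magnet-site skin events in the primary safety endpoint therefore rests on general AE enquiry and review, advised parent checks and incidental observation. The plausible effects are a lower recorded rate of mild skin events and detection that varies by site.

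The size cannot be derived from the documents. Under assumed sensitivities of 80%, 60% and 50%, the chance of seeing at least one event at the plan's 5.9% example rate falls from 95.2% to 91%, 84% and 78%. That range shows how far the stated figure depends on complete detection; it does not estimate the actual loss. It also assumes one common sensitivity across sites and subjects.

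**What to change.** At Visits 2, 3 and 4, as part of the AE review already required, have the site look at the implant and magnet site and record finding yes/no on the CRF. Any finding is then assessed as an AE under protocol Section 10.2. Add the item to the three visit lists and a matching row to the Schedule of Events. Visit 5 is optional: it lies outside the primary window and its list includes no processor handling. This changes how safety data are collected and leaves treatment and management unchanged.

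Cost: one CRF line and a brief look at three existing visits, with no extra staff. The recorded rate of mild skin events will probably rise, and the report should say that the site was inspected systematically. In return, a low skin-event rate would rest on a documented look at the site, and one source of artificial site differences would be reduced before the poolability analysis.
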